#### **6.1.2 Standard of Care Study Procedures**

The following procedures will be provided as standard of care:

1. Preoperative interview and evaluation of patients for indication for primary THA or TKA
2. Preoperative health assessment and medical clearance
3. THA or TKA
4. Inpatient stay following procedure
5. Post-operative follow-up appointments

### **6.2 Study Schedule**

Procedure	Screening/Visit 1 (SOC visit within - 3 months of surgery)	Surgery	Visit 2 (SOC visit within +2 months of surgery)
-----------	---	---------	--

Screening	X (Research only)		
Consent	X (Research Only)		
Medical History	X (SOC)		
Surgical History	X (SOC)		
Demographics	X (SOC)		
Distribute medication		X (Research Only)	
Collect pill bottle			X (Research Only)
Collect Adverse Events			X (Research Only)
Collect Questionnaires and peri-operative data (in-patient opioid consumption, Epworth and Stanford sleepiness scale, VAS Pain Scale)		X (Research Only)	X (Research Only)
Collect Sleep Diary			X (Research Only)

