## Protocol Summary

Title	MELATONIN USE AFTER PRIMARY TOTAL JOINT ARTHROPLASTY: A RANDOMIZED, DOUBLE BLIND, PLACEBO-CONTROLLED TRIAL
Brief Summary	The purpose of this study is to determine the effect of melatonin supplementation on patient sleep quality, length of stay, and opioid consumption following primary, unilateral, elective total hip or knee arthroplasty.
Phase	N/A
Objectives	The primary objective is improved sleep quality postoperatively
Methodology	Single Center, randomized, double-blind, placebo-controlled clinical trial
Endpoint	The primary endpoint will be enrollment and completion of the study of 256 patients as pre-determined by statistical analysis.
Study Duration	Approximately 12 months (post IRB approvals)
Participant Duration	We estimate each patient will need to participate for roughly 60 days
Duration of IP administration	Patients will take the melatonin or placebo for 14 days
Population	Sample size will be 252 patients, both male and female patients will be included, all adult patients undergoing primary elective TKA or THA will be included. No vulnerable populations will be enrolled
Study Sites	Langone Orthopedic Hospital, New York, NY NYU Brooklyn Hospital, Brooklyn, NY
Number of participants	256 participants
Description of Study Agent/Procedure	Melatonin is an over-the-counter sleep aid
Reference Therapy	None
Key Procedures	Pre- and postoperative sleep survey, survey on quality of sleep, patient reported outcome questionnaires, narcotic consumption and pain daily for 14 days postoperatively
Statistical Analysis	Descriptive statistics will be used to report baseline characteristics and primary study objectives

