### **3.2 Study Endpoints**

#### **3.2.1 Primary Study Endpoints**

The primary endpoint will be the Epworth Sleep Score for patients indicating the impact of melatonin on quality of sleep, including total hours of sleep and nighttime awakening. The ESS will be evaluated post-operatively from days 1-14.

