### **5.1.8 Tracking of Dose**

Patients will be encouraged to return the empty bottle at the 2 week postoperative visit.

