## **6 Study Procedures and Schedule**

### **6.1 Study Procedures/Evaluations**

#### **6.1.1 Study Specific Procedures**

- Medical history- a patient's medical history will be elicited during their pre-operative indication for surgery by their operative surgeon. This information will be then accessed via the EMR
- Medication history- current medications will be elicited during the patient's pre-operative indication for surgery by their operative surgery. This information will then be accessed via the EMR
- Physical examination- the patient's height and weight at each visit will be recorded, as well as a targeted physical musculoskeletal examination of the affected joint (ie hip for THA and knee for TKA). This information will then be accessed via the EMR
- Pre- and postoperative sleep survey,
- Survey on quality of sleep,
- Sleep diary
  - To be kept every day for the first 2 weeks
- VAS
- Opioid consumption will be measured based on in-patient pain medications given following surgery. This data will be pulled from Epic following discharge.

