### 6.2.2 Enrollment/Baseline

#### Enrollment/Baseline Visit (Visit 1)

- Review medical history to determine eligibility based on inclusion/exclusion criteria.
- Obtain informed consent of potential participant verified by signature on study informed consent form.
- Obtain and record vital signs, results of examinations, demographic information, medical history, medication history, alcohol and tobacco use history, and other assessments from the medical records.
- Record PROMIS – Sleep Disturbance

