### **8.4.4 Adherence and Retention Analyses**

Adherence to the study will be analyzed by collecting the pill bottles at the first postoperative visit.

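### The primary endpoint is the Epworth score over post-operative days 1–14, but no scheduled procedure obtains an Epworth score on any named day in that window

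*Combined protocol and SAP*

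**What the plan says.** Section 3.2.1 sets the window: "The ESS will be evaluated post-operatively from days 1-14". Section 8.1 tests the mean ESS over those days, section 8.2 sizes the trial on it, and section 8.4.1 compares the groups by repeated measures ANOVA within the hip and knee cohorts. None of these sections lists the assessment days or their number.

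The schedule in section 6.2 has one row that includes the ESS: "Collect Questionnaires and peri-operative data (in-patient opioid consumption, Epworth and Stanford sleepiness scale, VAS Pain Scale". It is marked under Surgery and under "Visit 2 (SOC visit within +2 months of surgery", and is blank at Visit 1.

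The visit descriptions in sections 6.2.2 and 6.2.3 do not name the Epworth scale. For sleep, Visit 1 has only "Record PROMIS – Sleep Disturbance". The surgery entry covers handing over the pill bottle. Visit 2 lists an unspecified sleepiness scale, PROMIS, VAS pain, the diary and opioid use. In section 6.1.1 the only item with a daily instruction is the sleep diary ("To be kept every day for the first 2 weeks"), and its contents are not described.

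Three other places bear on timing. The Protocol Summary lists "patient reported outcome questionnaires, narcotic consumption and pain daily for 14 days postoperatively". Section 5.1.8 says "Patients will be encouraged to return the empty bottle at the 2 week postoperative visit". Section 8.4.4 assesses adherence by "collecting the pill bottles at the first postoperative visit".

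**The concern.** A repeated measures analysis of days 1–14 needs at least two ESS values per patient from those days. The plan defines the window but gives no procedure that fills it. Staff could comply fully with the schedule and still leave the primary analysis without its data, and a score missed in the first two weeks cannot be recovered later.

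The ESS that is scheduled after discharge may be taken well after the 14-day course has ended, and at different times in different patients. It would then describe something other than the stated endpoint.

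The undefined days also leave the primary test open. The alternative in section 8.1 is a difference at any of the time points, those points are not listed, and section 8.4.7 treats multiplicity as not applicable. The days entering the test could be settled after the data are seen. The Wilcoxon rank sum sensitivity analysis in section 8.4.1 needs one value per patient, and the plan does not say which.

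**Working it through.** **Step 1. Required against scheduled.**

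| Source | What it gives for the ESS |
|---|---|
| 3.2.1, 8.1, 8.2 | Days 1–14; days and number of assessments not listed |
| 8.4.1 | Repeated measures ANOVA, so at least 2 values per patient |
| 6.2, Visit 1 | Not marked |
| 6.2, Surgery | Marked; before or after the operation not stated |
| 6.2, Visit 2 | Marked; any time up to 2 months |
| 6.2.2 and 6.2.3, visit text | Epworth not named |
| 6.1.1, daily diary | Not said to contain the ESS |

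The Surgery entry falls in the window only if it is completed after the operation, on day 1 or later. Section 11.3.2 allows enrolment once surgery is complete, so a post-operative entry is possible. Visit 2 falls in the window only if it happens by day 14, which the schedule does not require. ESS values certain to fall within days 1–14 are therefore 0, or 1 if the Surgery entry is a ward assessment.

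**Step 2. How late Visit 2 can be.** The Protocol Summary gives participation as roughly 60 days. Taking two months as 60 days, 60 − 14 = 46 days after the window closes. This is the permitted extreme, not an expected value.

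**Step 3. Whether the sample size shows the number of repeats.** Inputs from section 8.2: difference 2.65, SD 5.3, two-sided alpha 0.05, power 80%. Allocation is 1:1 (section 3.1).

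- Standardised difference: 2.65 / 5.3 = 0.5.
- Normal approximation: n = 2 × (1.960 + 0.842)² / 0.5² = 62.8, so 63 per group.
- Two-sample t-test: n = 63.77, so 64 per group, with power 80.1% at 64.

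The plan's 64 per group (128 per cohort) is reproduced exactly, by a comparison of one ESS value per patient. It carries no information on how many repeats were intended.

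**Step 4. Whether the number of repeats matters (illustration only).** The documents give no within-patient correlation. I assume compound symmetry, a constant difference of 2.65 and correlations ρ from 0.3 to 0.9. The SD of a patient's mean over m assessments is 5.3 × √[(1 + (m − 1)ρ) / m]. Power at 64 per group, by normal approximation:

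| Assessments m | ρ = 0.9 | ρ = 0.3 |
|---|---|---|
| 1 | 80.7% | 80.7% |
| 2 | 82.7% | 93.9% |
| 14 | 84.4% | 99.8% |

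Under these assumptions more repeats only add power. The problem is therefore not a shortfall in the sample size. It is that the design being analysed is not fixed.

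**The case against.** The strongest reply is that the protocol states the window in binding text, several times, and that the schedule is a list of when forms are collected, not of when they are completed. The diary is also marked only at Visit 2, yet it is plainly filled in daily. On that reading the ESS row, which likewise speaks of collecting, could refer to forms completed earlier. Section 8.1 refers to time points in the plural, the analysis is a repeated measures one, and the daily wording in the Protocol Summary can be read to cover the questionnaires. The bottle-return text in sections 5.1.8 and 8.4.4, with bottle collection scheduled at Visit 2, suggests that Visit 2 was meant to fall near day 14. Case report forms (section 9) and a manual of procedures (section 12.3) are mentioned but not supplied, and may hold the detail.

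Much of this stands as evidence of intent: repeated ESS measurement, possibly daily, was probably planned. It does not supply the instruction. The diary has an explicit daily direction and the ESS has none. Section 8.1 says each day for hours of sleep but not for the ESS. The Protocol Summary does not name the Epworth scale. A Visit 2 near day 14 would give one value, not a series. A manual may fill the gap, so the finding is limited to this document; even so, the days that enter the primary test belong in the protocol.

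**Conclusion.** The point holds, and the text needs correcting because it concerns whether the primary endpoint data will exist. The schedule and visit text secure 0 or 1 ESS values per patient within days 1–14, against the two or more that the planned analysis needs. The count assumes that staff work from the schedule and visit descriptions as written. The 46 days assumes two months is 60 days and is an outer limit. No loss of power is claimed: 64 per group is correct for one value per patient, and the calculation neither confirms nor excludes repeats.

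**What to change.** 1. Add to the section 6.2 schedule the ESS days that the primary analysis will use: either every day from 1 to 14, or named days ending at day 14.
2. State how the ESS is completed on those days (a diary page or a REDCap survey), with a recall period suited to the spacing.
3. State whether the Surgery ESS is pre-operative.
4. Name the Epworth scale in the visit descriptions, and bring the Protocol Summary and sections 3.2.1, 5.1.8, 6.2, 6.2.3, 8.1, 8.2, 8.4.1 and 8.4.4 into line with the chosen days.
5. State that an ESS taken at Visit 2 after day 14 does not enter the primary analysis.

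The cost is schedule and visit wording plus one diary page or survey. The extra burden on patients is small, and smaller with named days than with daily completion. Treatment and sample size are unchanged.

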### 6.2.1 Screening

Study subjects will be identified/recruited by all study investigators. Investigators will recruit subjects among their own patients who have been recommended to have a Total Hip or Knee Arthroplasty. Eligibility will be confirmed through a review of subject medical records. Investigators will reinforce with their patients that participation is voluntary, that they do not have to participate, and that their decision to not participate will not affect their care, now or in the future. During the course of the recruitment process, subjects will interact with all study personnel.

With access granted by MCIT, Study team will access data/records in EPIC for patients identified by study investigators as meeting the study criteria.

### 6.2.2 Enrollment/Baseline

#### Enrollment/Baseline Visit (Visit 1)

- Review medical history to determine eligibility based on inclusion/exclusion criteria.
- Obtain informed consent of potential participant verified by signature on study informed consent form.
- Obtain and record vital signs, results of examinations, demographic information, medical history, medication history, alcohol and tobacco use history, and other assessments from the medical records.
- Record PROMIS – Sleep Disturbance

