### **6.2.3 Intermediate Visits**

#### **TKA or THA Surgery**

- Give patients the pill bottle with the study drug or placebo pill.

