# **Statistical Considerations**

## **8.1 Statistical Hypotheses**

- Primary endpoint: The null hypothesis is that there is no difference between the melatonin and placebo group in the mean ESS score from days 1-14 postoperatively. The alternative hypothesis is that there is a difference between the melatonin and placebo group in the mean ESS score during any of these time points
- Secondary endpoints:
  - Hours of sleeping measured each day from days 1-14 for overnight sleep: The null hypothesis is that there is no difference between the melatonin and placebo group in the mean hours of sleeping at these time points. The alternative hypothesis is that there is a difference between the melatonin and placebo group in the mean hours of sleeping at these time points. Nighttime awakenings are those that require an additional dose of pain medication to go back to sleep.
  - Other secondary endpoints to be listed

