## **8.4 Description of Statistical Methods**

### **8.4.1 Analysis of the Primary Efficacy Endpoint**

The primary outcome, the ESS score measured at days 1-14 postoperatively for each group, will be summarized using means, standard deviation, median and inter quartile ranges. In the main analysis, the ESS score of the control and intervention group in either THA or TKA cohort will be compared using repeated measures ANOVA. Significant tests will be two-sided at significant level at 0.05.

The normality assumption of the primary efficacy outcome will be checked and strategies to transform the outcome variable will be considered. As a sensitivity analysis, the ANOVA will be replaced with the Wilcoxon rank sum test to ensure the robustness of the results.

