### **8.4.5 Baseline Descriptive Statistics**

Baseline characteristics including age, sex, ASA class, BMI, past medical and surgical history will be recorded by melatonin and placebo group for THA and TKA cohort separately. Summary statistics will be used, where means and standard deviations will be reported for continuous variables, and count and proportion will be calculated for categorical variables. Inferential tests to assess differences in baseline characteristics of the groups will be performed using ANOVA or the Wilcoxon rank sum test if the normality assumption does not hold for continuous variables, and the Chi-square test for categorical variables. All tests will be two-sided with a significance level at 0.05.

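### No pre-operative Epworth score is clearly scheduled and the primary analysis uses none, so each joint-specific comparison gives up precision that would be cheap to obtain

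*Combined protocol and SAP*

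**What the plan says.** **Endpoint and hypothesis.** Section 3.2.1 states "The ESS will be evaluated post-operatively from days 1-14". The null hypothesis in 8.1 is "no difference between the melatonin and placebo group in the mean ESS score from days 1-14 postoperatively". Both concern post-operative values only; neither uses a change from baseline.

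**Analysis.** Under 8.4.1, "the ESS score of the control and intervention group in either THA or TKA cohort will be compared using repeated measures ANOVA". No covariate is named. Section 8.3 keeps the hip and knee cohorts separate throughout.

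**What is collected before surgery.** Section 6.2.2 (Visit 1) lists one sleep instrument: "Record PROMIS – Sleep Disturbance". In the 6.2 schedule, the row "Collect Questionnaires and peri-operative data (in-patient opioid consumption, Epworth and Stanford sleepiness scale, VAS Pain Scale") is blank at Screening/Visit 1 and marked at Surgery and at Visit 2. The Surgery entry in 6.2.3 has a single item, "Give patients the pill bottle with the study drug or placebo pill", with no questionnaire and no timing. The Protocol Summary and 6.1.1 both list a sleep survey before and after surgery, but neither names the instrument.

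**What is reported at baseline.** Section 8.4.5 covers "Baseline characteristics including age, sex, ASA class, BMI, past medical and surgical history". No sleep score is named.

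**The concern.** A patient's sleepiness before surgery is likely to be correlated with sleepiness in the two weeks after it. A score on the same scale, taken before treatment, is therefore the natural covariate for the primary comparison. Here it is unclear whether such a score will exist, and no planned analysis would use it if it did.

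Three things are at stake:

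- **Precision.** Each cohort is analyzed alone with 64 per arm, so gains within a cohort matter.
- **Chance imbalance.** Randomization is not stratified by surgery type (8.5.1). An uneven split in baseline sleepiness within a cohort would go uncorrected, and might not be visible on the primary scale.
- **Interpretation.** Section 4.2 excludes insomnia and users of prescription sleep aids. Without a baseline ESS, it would be hard to tell a null result from a sample with little room to improve.

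The gap has to be closed prospectively, because a pre-operative score that was not collected cannot be recovered.

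**Working it through.** **Step 1: is a pre-operative ESS planned?**

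| Place | What it settles |
|---|---|
| 6.2.2, Visit 1 | PROMIS only; ESS not listed |
| 6.2, Visit 1 column | Epworth row blank |
| 6.2, Surgery column | Epworth row marked; before or after the operation not stated |
| 6.2.3, Surgery | Dispensing only |
| 6.1.1 and Protocol Summary | A pre-operative sleep survey is intended; instrument not named |

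The Surgery mark also covers in-patient opioid consumption, which 6.1.1 measures after surgery, so the mark alone cannot be read as a baseline. A pre-operative ESS is neither clearly scheduled nor ruled out. If the Surgery ESS is pre-operative, 8.4.1 still does not use it and 8.4.5 does not name it.

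**Step 2: reproduce the plan's sample size.** Inputs from 8.2: difference 2.65, SD 5.3, two-sided alpha 0.05, power 80%. The standardized difference is 2.65/5.3 = 0.50. The two-sample t-test (equivalently a two-group ANOVA) needs 63.77, so 64 per arm; power at 64 is 80.1%. The normal approximation gives 63. The stated 64 is reproduced, and it rests on the full unadjusted SD.

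**Step 3: chance imbalance at baseline.** Assume baseline ESS also has SD 5.3; 8.2 gives that figure for the endpoint only.

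- SE of the difference in baseline means = 5.3 × √(2/64) = 0.94; 95% range ±1.96 × 0.937 = ±1.84.
- P(imbalance above 1 point in either direction) = 2 × [1 − Φ(1/0.937)] = 0.286, about 29% of such cohorts.
- With equal SDs, an imbalance shifts the unadjusted estimate by r times its size, where r is the pre/post correlation. A 1-point imbalance shifts it by 0.3 to 0.7 points for r = 0.3 to 0.7, which is 11% to 26% of 2.65. An imbalance at the 95% limit shifts it by 0.55, 0.92 or 1.29 points for r = 0.3, 0.5 or 0.7.

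**Step 4: gain from adjustment.** Residual SD = 5.3 × √(1 − r²); the variance cut is r²; the 95% CI half-width is 1.96 × SD × √(2/64). The documents give no r, so a range is shown.

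| Assumed r | Variance cut | Residual SD | CI half-width | Power at 64 per arm | n per arm for 80% |
|---|---|---|---|---|---|
| none (plan) | 0% | 5.30 | 1.84 | 80.1% | 64 |
| 0.3 | 9% | 5.06 | 1.75 | 83.7% | 59 |
| 0.5 | 25% | 4.59 | 1.59 | 90.0% | 49 |
| 0.7 | 49% | 3.79 | 1.31 | 97.6% | 34 |

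The table treats the ESS as a single post-operative measure, as the plan's own calculation does. If a fraction f of patients has no baseline, the variance cut is roughly (1 − f)r², so the figures are upper limits.

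**The case against.** The strongest reply is that nothing in the plan fails without adjustment. Allocation is 1:1, blocked and double-blind, so the unadjusted comparison is unbiased in expectation and chance imbalance is already in its standard error. The sample size assumes the unadjusted SD, so the stated 80% is not breached. All of this stands.

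Two stronger readings are tempting, and the documents support neither:

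- *The ESS has no pre-operative value at all.* The Epworth row is marked at Surgery, and a pre-operative sleep survey is listed in two places. The documents are ambiguous rather than silent.
- *The melatonin effect is confounded with pre-existing sleepiness, or a baseline imbalance enters the estimate in full.* Randomization rules out the first as systematic bias. The second ignores the factor r: the 29% in Step 3 describes baseline differences, not errors of that size in the treatment effect.

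The reply also has fair points on the size of the gain. The correlation is not in the documents. The SD of 5.3 comes from a source whose title places it in obstructive sleep apnea, and it may not describe this population. The planned analysis is repeated measures, not a single measure. The list in 8.4.5 begins with a word that leaves it open, and PROMIS is recorded at both Visit 1 and Visit 2, so baseline sleep is not wholly unobserved; it is unobserved on the primary scale.

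Finally, 11.3.2 lets patients approached on the day of surgery enroll once the operation is over, and requires consent before study procedures. No pre-operative ESS can be obtained as a study procedure from them. This limits the gain but does not remove it.

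**Conclusion.** The point holds as a lost, inexpensive improvement and an ambiguity to resolve. It is not a bias, and planned power is not short. No pre-operative ESS is clearly scheduled, and no analysis uses one on any reading of the schedule. Any non-zero pre/post correlation gives some gain in precision: about 84% to 98% power instead of 80% for r between 0.3 and 0.7.

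These sizes rest on an assumed r, on SD 5.3 applying at baseline as well as after surgery (for the carry-through of an imbalance), on a single-measure calculation, and on a baseline being available for everyone. The missing covariate and the undefined timing of the Surgery ESS rest on the text alone. This should be changed, but the trial is not invalid without it.

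**What to change.** 1. **6.2.2 and 6.2:** add the ESS to Visit 1 beside PROMIS Sleep Disturbance, completed before allocation and first dose, and mark it in the schedule.
2. **6.2 and 6.2.3:** state whether the Surgery ESS is pre-operative, and reconcile these sections with 6.1.1 and 6.2.2, naming the instrument in the pre-operative sleep survey. If the Surgery ESS is pre-operative, say that it serves as baseline for anyone without a Visit 1 value.
3. **8.4.1:** include pre-operative ESS as a covariate in the repeated-measures comparison of days 1-14 within each cohort. Add a missing-baseline indicator for patients enrolled after surgery (11.3.2), so that all randomized patients stay in as 8.3 requires.
4. **8.4.5:** report pre-operative ESS and PROMIS by arm in each cohort, with the number missing.

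The cost is one short questionnaire at a visit that already takes one, one schedule mark and one model term with its indicator. No extra patients are needed. The downsides are a few minutes of patient time and no baseline for patients consented after surgery.
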